8.3. Clinical Laboratory Tests

8.3.1. Laboratory Value Definitions

Laboratory values and change from baseline values will be summarized descriptively by visit. The baseline value will be determined using the nonmissing values collected before the first dose using the priority defined in [Table 4](#). The last record before administration in the highest priority will be considered the baseline record. For baseline laboratory candidates with the same date and time in the same priority category, additional rules may be provided after consultation with the medical monitor to delineate which value will be defined as baseline.

Table 4: Identification of Baseline Record

Priority	Laboratory Visit	Central or Local Laboratory
1	Scheduled	Central
2	Scheduled	Local
3	Unscheduled	Central
4	Unscheduled	Local

Laboratory test values will be assessed for severity based on the numerical component of CTCAE v5.

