8.1.2. Screening Procedures

Screening is the interval between signing the ICF and the day the participant is enrolled in the study (Cycle 1 Day 1). Screening may not exceed 28 days. Assessments that are required to demonstrate eligibility may be performed over the course of 1 or more days during the screening process.

Procedures conducted as part of the participant's routine clinical management (eg, blood count, imaging study) and obtained before signing of informed consent may be used for screening or baseline purposes provided the procedure meets the Protocol-defined criteria and has been performed in the timeframe of the study (ie, within 28 days of Cycle 1 Day 1). For participants who are enrolled in the study, information associated with eligibility requirements must be entered into the appropriate eCRF pages.

Results from the screening visit evaluations will be reviewed to confirm eligibility before enrollment or the administration of study drug. Tests with results that fail eligibility requirements may be repeated once during screening if the investigator believes the results to be in error. For screening assessments that are repeated, the most recent available result before treatment assignment will be used to determine eligibility. Additionally, a participant who fails screening may repeat the screening process 1 time if the investigator believes there has been a change in eligibility status (eg, after recovery from an infection).

See Sections [5.4](#) and [5.5](#) for information regarding screen failures and replacement of participants, respectively.

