4.1.3. Baseline Value

Baseline is the last nonmissing measurement obtained before the first administration of study treatment (INCB001158 or daratumumab SC), unless otherwise defined.

When scheduled assessments and unscheduled assessments occur on the same day and the time of the assessment or time of first dose is not available, use the following convention to determine baseline:

- If both a scheduled and an unscheduled visit are available on the day of the first dose and the time is missing, use the scheduled assessment as baseline.
- If all scheduled assessments are missing on the day of the first dose and an unscheduled assessment is available, use the unscheduled assessment as baseline.

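### SAP Table 4 ranks laboratory records by visit type before date, so a superseded screening value can become baseline when the repeat is recorded as unscheduled and the Cycle 1 Day 1 draw is waived

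*SAP*

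**What the plan says.** The SAP has two baseline rules. The general one, in SAP 4.1.3, goes by date: "Baseline is the last nonmissing measurement obtained before the first administration of study treatment", unless another definition is given. It prefers scheduled records only as a narrow convention: "If both a scheduled and an unscheduled visit are available on the day of the first dose and the time is missing", the scheduled one is taken.

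For laboratory data, SAP 8.3.1 gives another definition: "The baseline value will be determined using the nonmissing values collected before the first dose using the priority defined in" Table 4. That table lists scheduled central, scheduled local, unscheduled central and unscheduled local, in that order, and has no date criterion. The selection is then: "The last record before administration in the highest priority will be considered the baseline record". Nothing removes a result that was later superseded or that failed an entry limit.

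Protocol 8.1.2 provides for repeats: "Tests with results that fail eligibility requirements may be repeated once during screening if the investigator believes the results to be in error". After a repeat, "the most recent available result before treatment assignment will be used to determine eligibility".

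Two other protocol provisions matter. Section 8.3.7 requires screening laboratory tests done more than 7 days before C1D1 to be repeated, and Day 1 samples to be taken before dosing. Protocol Table 5 schedules a C1D1 draw for chemistry, hematology, lipids, urinalysis and thyroid. It waives that draw if the screening assessment was within the preceding 7 days, unless a clinically significant change is suspected.

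**The concern.** Eligibility and baseline can rest on different results for the same participant. The protocol admits the participant on the most recent value, while the SAP can measure change from the value that the protocol set aside.

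There are two routes. In the first, a failed screening test is repeated and passes. In the second, no test fails, but screening laboratory tests are older than 7 days and are repeated before C1D1. The superseded value may then be up to 28 days old, the length of the screening window. In both routes the repeat must be recorded as unscheduled and no later scheduled pre-dose sample may exist.

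Safety is the only formal analysis left, because the SAP limits efficacy to listings. Laboratory baseline feeds change from baseline by visit (Tables 3.3.1.1 and 3.3.1.2) and treatment-emergent worsening (Tables 3.3.3.4 and 3.3.3.5). Phase 1 is shown by dose level, with 3 to 9 evaluable participants per level before any backfill. One wrong baseline is then between 1/9 = 11% and 1/3 = 33% of a cell. Backfill participants, and treated participants who are not evaluable for dose-limiting toxicity, would lower that share.

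**Working it through.** The plan states no figure to reproduce. The check applies both rules to the same pre-dose records.

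**Rules**
- Table 4 rule (SAP 8.3.1): find the best priority class present, then take the latest record in it.
- Date rule (SAP 4.1.3): take the latest nonmissing pre-dose record.

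**Inputs**
- Entry limit, from Protocol Table 13: neutrophil count below 1.0 x 10^9/L is excluded.
- Assumed values, x 10^9/L: failed screening 0.9, repeat 1.6, C1D1 draw 1.5, on-treatment value 0.8.
- All records are local. Change = on-treatment value minus baseline.
- In sequence 2, the repeat within 7 days is assumed to satisfy the C1D1 waiver.

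| Sequence | Table 4 baseline | Date-rule baseline | Change, Table 4 | Change, date rule |
|---|---|---|---|---|
| 1. Fails Day -5 (scheduled); repeat Day -2 unscheduled; C1D1 waived | 0.9 | 1.6 | 0.8 - 0.9 = -0.1 | 0.8 - 1.6 = -0.8 |
| 2. Fails Day -20 (scheduled); repeat Day -4 unscheduled; C1D1 waived on the repeat | 0.9 | 1.6 | -0.1 | -0.8 |
| 3. Fails Day -20 (scheduled); repeat Day -15 unscheduled; C1D1 drawn | 1.5 | 1.5 | 0.8 - 1.5 = -0.7 | -0.7 |
| 4. Fails Day -5 (scheduled); repeat Day -2 under the scheduled visit; C1D1 waived | 1.6 | 1.6 | -0.8 | -0.8 |
| 5. Fails Day -5 (scheduled); repeat Day -2 unscheduled; C1D1 drawn anyway | 1.5 | 1.5 | -0.7 | -0.7 |

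The rules differ only in sequences 1 and 2. The five sequences show when the rule fails; they say nothing about how often.

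**Size of the error.** Error in change = (Y - baseline by Table 4) - (Y - baseline by date) = baseline by date - baseline by Table 4. The on-treatment value Y cancels. Here it is 1.6 - 0.9 = 0.7 x 10^9/L at every visit. An assumed ALT example runs the other way on the scale. With 2.8 x ULN at screening (limit 2.5 x ULN), 1.2 on repeat and 2.7 on treatment, the change by date is 2.7 - 1.2 = +1.5 x ULN. By Table 4 it is 2.7 - 2.8 = -0.1 x ULN.

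**Direction.** Protocol Section 5 bars eligibility waivers. For an analyte with a Table 13 limit, the repeat of a properly enrolled participant therefore lies on the acceptable side and the failed value on the other. Whenever Table 4 picks the failed value, baseline is too abnormal and deterioration is understated. In the second route, where nothing failed, the direction is not fixed.

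**The case against.** The strongest answer is that the effect is conditional. Neither document says how a screening repeat is coded. Protocol 8.1.2 describes it as taking place during screening, so it may sit under the scheduled screening visit, and the Table 4 rule then picks the repeat. If a C1D1 sample is drawn, it is the latest scheduled record and becomes baseline. This stands. A reader might infer that every participant with a repeated failed test gets a wrong baseline, or that this happens often; the documents support neither.

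A reader might also infer that the ALT example proves an undercount of worsening. It does not. Worsening is judged on CTCAE v5 grades, whose cut-offs are not in the documents, so only an error in numerical change is shown.

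Nor does the SAP contradict itself: 4.1.3 yields to a specific definition, and 8.3.1 is one. SAP Table 5 uses the same source order after baseline, so there is a consistent convention behind it. That explains the ranking but gives no reason to prefer an outdated value.

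Finally, the impact is limited. The safety endpoint is adverse events, the laboratory summaries are descriptive, and listings cover individual values. This lowers the stakes, but listings do not correct the tables.

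**Conclusion.** The defect is a stated rule that can select the wrong record. It operates when three things coincide: a screening repeat exists, it is recorded as unscheduled, and no later scheduled pre-dose sample was taken. The superseded screening value then replaces the last pre-dose value, and the error in change equals the difference between the two at every visit. Where the superseded value failed a Table 13 limit, the error hides deterioration, and Tables 3.3.3.4 and 3.3.3.5 may undercount worsening. A changed grade is possible but not demonstrated.

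The number of participants affected cannot be determined from the documents and may be zero. The conclusion assumes that some repeats are recorded as unscheduled. This is plausible, because Protocol Table 5 has a single screening column and Protocol 8.6 provides for unscheduled visits, but it is not stated. The change is worth making because it is cheap and safety is what the study will report.

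**What to change.** In SAP 8.3.1, define laboratory baseline as the nonmissing value with the latest date (and time, if known) before first administration of study treatment, whether scheduled or unscheduled, consistent with SAP 4.1.3. Use the Table 4 order only to choose among records on the same date when time does not separate them. This corrects sequences 1 and 2 and leaves the other three unchanged. It also agrees with the first-dose-day convention in 4.1.3, since Table 4 puts scheduled records first.

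A narrower alternative is to state that screening repeats count as scheduled records. That closes the same gap but depends on identifying those repeats in the data.

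The cost is one SAP sentence and one line of derivation code. There is a small downside: for analytes measured at both laboratories, baseline may occasionally come from a different laboratory than the postbaseline record. This should be uncommon, because Protocol 8.3.7 assigns most safety tests to the local laboratory, although Protocol 8.3.7.2 also mentions shipping chemistry samples to a central one. Keeping the Table 4 order for same-date records preserves the central preference where it does no harm.

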8.3.2. Laboratory Value Summaries

All test results and associated normal ranges from central laboratories will be reported in SI units. Any laboratory test results and associated normal ranges from local laboratories will be converted to SI units.

When there are multiple nonmissing laboratory values for a participant's particular test within a visit window, the convention described in [Table 5](#) will be used to determine the record used for by-visit tabulations and summaries.

Table 5: Identification of Records for Postbaseline By-Visit Summaries

Priority	Laboratory Visit	Central or Local Laboratory	Proximity to Visit Window	Tiebreaker
1	Scheduled	Central	In-window	Use smallest laboratory sequence number
2	Scheduled	Local	In-window	
3	Unscheduled	Central	In-window	
4	Unscheduled	Local	In-window	
5	Scheduled	Central	Out-of-window	
6	Scheduled	Local	Out-of-window	

For coagulation and urinalysis laboratory values, listings will be provided.

Numeric chemistry and hematology laboratory values will be summarized descriptively in SI units, and non-numeric test values will be tabulated when necessary.

Severity grades will be assigned to laboratory test values based on the numerical component of CTCAE v5. The number of participants who experienced worsening of laboratory abnormalities will be summarized by maximum severity.

In cases where differentials of hematology parameters are obtained without corresponding absolute count data, efforts will be made to investigate if the conversion to an absolute value will lead to additional abnormalities. This will be discussed with the clinical team regarding appropriate documentation and action.

8.4. Vital Signs

Values at each scheduled visit, change, and percent change from baseline for vital signs, including systolic blood pressure, diastolic blood pressure, pulse, temperature, respiratory rate, and weight, will be summarized descriptively.

Normal ranges for vital sign values are defined in [Table 6](#). For participants exhibiting vital sign abnormalities, the abnormal values will be listed along with their assigned treatment group. Alert vital signs are defined as an absolute value outside the defined normal range and percentage change greater than 25%. Note that the definition of alert vital signs does not apply for body temperature and weight. The abnormal values for participants exhibiting alert vital sign abnormalities will be listed.

Table 6: Normal Vital Sign Values

Parameter	High Threshold	Low Threshold
Systolic blood pressure	≤ 155 mmHg	≥ 85 mmHg
Diastolic blood pressure	≤ 100 mmHg	≥ 40 mmHg
Pulse	≤ 100 bpm	≥ 45 bpm
Temperature	$\leq 38^{\circ}\text{C}$	$\geq 35.5^{\circ}\text{C}$
Respiratory rate	≤ 24 breaths/min	≥ 8 breaths/min

8.5. Electrocardiograms

Twelve-lead ECGs including PR, RR, QT, QRS, and QTcF intervals will be obtained for each participant during the study. Values at each scheduled visit, change, and percentage change from baseline will be summarized for each ECG parameter. Baseline will be determined as the average of all nonmissing values before the first administration of INCB001158 or daratumumab SC.

Electrocardiogram results will be reviewed for clinically notable abnormalities according to the investigator. Electrocardiogram values will also be considered abnormal if the absolute percentage change from baseline is more than 25% (30% for QRS interval). Participants exhibiting ECG abnormalities will be listed with study visit and assigned treatment group. Outliers of QT and QTcF values, defined as absolute values > 450 milliseconds, > 500 milliseconds, or change from baseline > 30 milliseconds, will be summarized.

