10.4.2.2. Clinical Laboratory Tests

Laboratory test values outside the normal range will be assessed for severity based on the normal ranges for the clinical reference laboratory. The incidence of abnormal laboratory values and shift tables relative to baseline will be tabulated.

Laboratory data will be classified into Grades 1 through 5 using CTCAE v5. The following summaries will be produced for the laboratory data:

- Number and percentage of participants with worst postbaseline CTCAE grade (regardless of baseline value). Each participant will be counted only for the worst grade observed postbaseline.
- Shift tables from baseline to the worst postbaseline value using CTCAE grade.

For laboratory parameters where CTCAE grades are not defined, shift tables to the worst postbaseline value using the low/normal/high classifications based on laboratory reference ranges.

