10.4.2.4. Electrocardiograms

Descriptive statistics and mean change from baseline will be determined for each ECG parameter at each assessment time. Electrocardiogram results will be reviewed for clinically notable abnormalities according to predefined criteria (see [Table 29](#)). Participants exhibiting clinically notable ECG abnormalities will be listed.

Table 29: Criteria for Clinically Notable Electrocardiogram Abnormalities

[figure not shown]
Parameter	High Threshold	Low Threshold
QTcF	> 470 ms	< 295 ms
PR	> 220 ms	< 75 ms
QRS	> 120 ms	< 50 ms
QT	> 500 ms	< 300 ms
RR	> 1330 ms	< 600 ms

QTcF = Fridericia correction.

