2.2. Study Objectives and Endpoints

[Table 1](#) presents the objectives and endpoints.

Due to early termination decision following recruitment challenge (no safety-related concerns), primary safety analyses but no efficacy analyses will be performed due to insufficient number of participant enrolled in Phase 2.

Table 1: Objectives and Endpoints

Objectives	Endpoints
Primary	
Phase 1: To determine the safety, tolerability, and RP2D of INCB001158 in combination with daratumumab SC.	Safety and tolerability determined by monitoring the frequency, duration, and severity of AEs.
Phase 2: To compare the ORR of the RP2D of INCB001158 in combination with daratumumab SC to daratumumab SC monotherapy.	ORR, defined as the proportion of participants with a documented response PR or better, as per IMWG criteria.
Secondary	
Phase 1: To determine the efficacy of INCB001158 in combination with daratumumab SC.	ORR, defined as the proportion of participants with a documented response PR or better, as per IMWG criteria.
Phase 2: To determine the safety and tolerability of INCB001158 monotherapy at RP2D, and to compare the safety and tolerability and RP2D of INCB001158 in combination with daratumumab SC to daratumumab SC monotherapy	Safety and tolerability determined by monitoring the frequency, duration, and severity of AEs.
Phase 1: To determine the efficacy of INCB001158 in combination with daratumumab SC. Phase 2: To estimate the efficacy of INCB001158 monotherapy, and to compare the efficacy of INCB001158 in combination with daratumumab SC to daratumumab SC monotherapy.	
• TTR, defined as the time from the first dose of study drug to the first documented response PR or better, as per IMWG criteria.• DOR, defined as time from first documented response PR or better, as per IMWG criteria, until date of disease progression or death, whichever occurs first.• PFS, defined as the duration from the date of first dose of study drug until either PD, as per IMWG criteria, or death, whichever occurs first.• MRD, defined as the percentage of MRD-negative participants.• OS, defined as the time from the first dose of study drug to death from any cause.

Table 1: Objectives and Endpoints (Continued)

Objectives	Endpoints

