8.2.4. Adverse Event Summaries

An overall summary of AEs by dose level for Phase 1 and by treatment group for Phase 2 using the FAS population as applicable will include the following:

- Number (%) of participants reporting any TEAEs
- Number (%) of participants reporting any serious TEAEs
- Number (%) of participants reporting any Grade 3 or higher TEAEs
- Number (%) of participants who had a fatal TEAE
- Number (%) of participants who had a TEAE related to INCB001158
- Number (%) of participants who had a TEAE related to daratumumab SC
- Number (%) of participants who had a TEAE related to INCB001158 and/or daratumumab SC
- Number (%) of participants who had a Grade 3 or higher TEAE related to INCB001158
- Number (%) of participants who had a Grade 3 or higher TEAE related to daratumumab SC
- Number (%) of participants who had a Grade 3 or higher TEAE related to INCB001158 and/or daratumumab SC
- Number (%) of participants who had a serious TEAE related to INCB001158
- Number (%) of participants who had a serious TEAE related to daratumumab SC
- Number (%) of participants who had a serious TEAE related to INCB001158 and/or daratumumab SC

- Number (%) of participants who had a TEAE leading to temporary interruption of INCB001158
- Number (%) of participants who had a TEAE leading to INCB001158 dose reduction
- Number (%) of participants who had a TEAE leading to permanent discontinuation of INCB001158
- Number (%) of participants who had an irAE

The following summaries will be produced by MedDRA term for the Phase 1 and Phase 2 FAS population (if 10 or fewer participants appear in a table, a listing may be appropriate):

- Summary of TEAEs by SOC and PT
- Summary of TEAEs by PT in decreasing order of frequency
- Summary of Grade 3 or higher TEAEs by PT in decreasing order of frequency
- Summary of serious TEAEs by PT in decreasing order of frequency
- Summary of INCB001158 treatment-related TEAEs by PT in decreasing order of frequency
- Summary of Grade 3 or higher INCB001158 treatment-related TEAEs by PT in decreasing order of frequency
- Summary of TEAEs with a fatal outcome by SOC and PT
- Summary of TEAEs leading to INCB001158 dose reduction by PT in decreasing order of frequency
- Summary of TEAEs leading to INCB001158 dose interruption by PT in decreasing order of frequency
- Summary of TEAEs leading to discontinuation of INCB001158 by PT in decreasing order of frequency

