10.1. Changes to Protocol-Defined Analyses

As a result of an early-termination decision following a recruitment challenge (no safety-related concerns), primary safety analyses but no efficacy analyses will be performed due to an insufficient number of participants enrolled in Phase 2. Listings of efficacy data will be provided.

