3.2.8	Summary of Treatment-Emergent Adverse Events Leading to INCB001158 Dose Reduction by MedDRA Preferred Term in Decreasing Order of Frequency	FAS	
3.2.9	Summary of Treatment-Emergent Adverse Events Leading to INCB001158 Dose Interruption by MedDRA Preferred Term in Decreasing Order of Frequency	FAS	
3.2.10	Summary of Treatment-Emergent Adverse Events Leading to Discontinuation of INCB001158 by MedDRA Preferred Term in Decreasing Order of Frequency	FAS	
3.3.1.1	Summary of Laboratory Values - Hematology	FAS	X
3.3.1.2	Summary of Laboratory Values - Chemistry	FAS	X
3.3.3.4	Treatment-Emergent Worsening of Laboratory Abnormalities - Hematology	FAS	X
3.3.3.5	Treatment-Emergent Worsening of Laboratory Abnormalities - Chemistry	FAS	X
3.4.1	Summary of Systolic Blood Pressure	FAS	X
3.4.2	Summary of Diastolic Blood Pressure	FAS	X
3.4.3	Summary of Pulse	FAS	X
3.4.4	Summary of Respiratory Rate	FAS	X
3.4.5	Summary of Body Temperature	FAS	X
3.4.6	Summary of Body Weight	FAS	X
3.5.1	Summary of PR Interval (ms) From 12-Lead ECG	FAS	X
3.5.2	Summary of QRS Interval (ms) From 12-Lead ECG	FAS	X
3.5.3	Summary of QT Interval (ms) From 12-Lead ECG	FAS	X
3.5.4	Summary of QTcF Interval (ms) From 12-Lead ECG	FAS	X
3.5.5	Summary of RR Interval (ms) From 12-Lead ECG	FAS	X
3.5.6	Summary of Heart Rate (bpm) From 12-Lead ECG	FAS	X
3.5.7	Summary of Outliers of QT and QTcF Interval Values (ms) From 12-Lead ECG	FAS	X

Listings

Listing No.	Title
2.1.2.x	Participant Enrollment and Disposition Status
2.2.1.x	Participant Inclusion and Exclusion Criteria Violations
2.2.2.x	Protocol Deviations
2.3.1.x	Analysis Populations
2.4.1.x	Demographics and Baseline Characteristics
2.4.2.x	Baseline Disease Characteristics
2.4.3.x	Prior Radiation Treatment
2.4.4.x	Prior Therapy for Disease Under Study
2.4.5.x	Prior Surgery or Surgical Procedure
2.4.6.x	Medical History
2.4.7.x	Prior and Concomitant Medications
2.4.8.x	Post-Treatment Anticancer Therapy
2.5.1.x	Study Drug Administration for INCB001158
2.5.2.x	Study Drug Compliance for INCB001158
2.5.3.x	Study Drug Administration for Daratumumab SC
2.6.1.x	Overall Response Assessments and Best Overall Response Under IMWG Criteria
2.6.2.x	Efficacy Endpoints (TTR, DoR, PFS, and OS)
2.6.3.x	ECOG Status
2.6.4.x	Clinical Laboratory Values – Chemistry, SPEP
2.6.5.x	Clinical Laboratory Values – Immunology
2.6.6.x	Clinical Laboratory Values – Immunology, Free Light Chains
2.6.7.x	Clinical Laboratory Values – Immunology, Immunofixation

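### SAP 10.1 declares only the loss of efficacy analyses, yet the SAP also replaces the protocol's ECG limits and drops its laboratory worst-grade and shift tables without recording either change.

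*SAP*

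**What the plan says.** **Declared change.** SAP 10.1 records one departure from the protocol: "primary safety analyses but no efficacy analyses will be performed due to an insufficient number of participants enrolled in Phase 2". It adds: "Listings of efficacy data will be provided". It mentions no change to a safety analysis.

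**ECG.** Protocol 10.4.2.4 states: "Electrocardiogram results will be reviewed for clinically notable abnormalities according to predefined criteria". The criteria are the absolute limits in Table 29, and participants who breach them are to be listed. SAP 8.5 states: "Electrocardiogram results will be reviewed for clinically notable abnormalities according to the investigator". It also treats a value as abnormal if it changes from baseline by more than 25% (30% for QRS), and it summarizes QT and QTcF outliers (above 450 ms, above 500 ms, or a change above 30 ms). Table 29 is neither repeated nor cited.

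**Laboratory.** Protocol 10.4.2.2 requires counts by worst postbaseline CTCAE grade whatever the baseline, and "Shift tables from baseline to the worst postbaseline value using CTCAE grade". Tests without CTCAE grades get low/normal/high shift tables. SAP 8.3.2 plans descriptive summaries and counts of participants whose abnormalities worsened, by maximum severity. In Appendix A these are Tables 3.3.1.1, 3.3.1.2, 3.3.3.4 and 3.3.3.5, for hematology and chemistry. No shift table or worst-grade-regardless-of-baseline table appears.

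**Smaller items.** SAP Table 1 still carries "MRD, defined as the percentage of MRD-negative participants", but Listing 2.6.2 is titled "Efficacy Endpoints (TTR, DoR, PFS, and OS" (closing bracket omitted here) and no other listing names MRD. SAP 8.2.4 calls for "Summary of serious TEAEs by PT in decreasing order of frequency", and SAP 8.5 says participants with ECG abnormalities will be listed. Appendix A, as supplied, contains neither display.

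**The concern.** With efficacy analyses withdrawn, safety is the only formal analysis left in this study. The SAP is dated 19 APR 2022 and is based on Protocol Amendment 3 (01 DEC 2021), which says that enrollment had already been terminated. In an open-label study, safety criteria that change at that stage should be visible and justified.

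The stated reason for the SAP's changes, too few Phase 2 participants for efficacy, does not explain a different ECG criterion or a different laboratory table. Nor does the SAP set aside the protocol's fixed limits as a general policy. It keeps the vital-sign limits of Protocol Table 28 as the bounds of the normal ranges in SAP Table 6, and it plans an abnormal vital-sign listing. Only the ECG limits disappear. A reader comparing the study report with the protocol would find abnormality lists and tables built on other rules, with nothing in SAP 10.1 to say so.

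**Working it through.** **1. When does the SAP percentage rule catch a Table 29 breach?**

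Inputs: the limits in Protocol Table 29, and the change fraction c from SAP 8.5 (0.25, or 0.30 for QRS). A value at a high limit H reaches the rule only if baseline is below H/(1 + c). A value at a low limit L reaches it only if baseline is above L/(1 − c).

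| Interval | High limit (ms) | Baseline must be below | Low limit (ms) | Baseline must be above |
|---|---|---|---|---|
| PR | 220 | 220/1.25 = 176.0 | 75 | 75/0.75 = 100.0 |
| QRS | 120 | 120/1.30 = 92.3 | 50 | 50/0.70 = 71.4 |
| RR | 1330 | 1330/1.25 = 1064.0 | 600 | 600/0.75 = 800.0 |
| QTcF | 470 | 470/1.25 = 376.0 | 295 | 295/0.75 = 393.3 |
| QT | 500 | 500/1.25 = 400.0 | 300 | 300/0.75 = 400.0 |

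Illustrations:
- PR 190 to 225 ms: (225 − 190)/190 = 18.4%. Above 220 ms, so notable under Table 29, but below the 25% rule.
- QRS 100 to 125 ms: 25/100 = 25.0%. Above 120 ms, so notable under Table 29, but below the 30% rule.

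Under SAP 8.5, each is listed as abnormal only if the investigator calls it notable.

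**2. What else in the SAP covers those limits?**

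- *High QTcF:* every value above 470 ms is also above 450 ms, so it enters the outlier table (Table 3.5.7), although the 470 ms cut is not shown separately.
- *High QT:* the 500 ms limit is kept exactly.
- *RR:* SAP Table 6 treats pulse above 100 or below 45 bpm as abnormal. In RR terms, 60,000/100 = 600 ms and 60,000/45 = 1333 ms, against 600 and 1330 ms in Table 29. The source is pulse rather than the ECG, but the rate limits are nearly the same, and abnormal values are listed.
- *High PR and QRS, and low PR, QRS, QT and QTcF:* no absolute check remains. The outlier rules for QT and QTcF look only upward.

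**3. Laboratory tables side by side**

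| Protocol 10.4.2.2 | SAP 8.3.2 and Appendix A |
|---|---|
| Worst postbaseline CTCAE grade, regardless of baseline | Not planned; worsening only |
| CTCAE shift, baseline to worst value | Not planned as a shift table |
| Low/normal/high shift for ungraded tests | No categorical table planned |

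The displays are not interchangeable. A participant at Grade 2 both at baseline and at worst postbaseline counts in the protocol's worst-grade table but has not worsened. Participants moving from Grade 1 to 3 and from Grade 2 to 3 fall in different shift cells, but both have a maximum severity of Grade 3.

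**The case against.** The best reply is that little is hidden. All ECG values are in Listing 2.8.3.1 and are summarized by interval in Tables 3.5.1 to 3.5.6. Abnormal hematology and chemistry values have their own listings (2.8.1.5 and 2.8.1.6). In a study stopped for low recruitment, breaches and grade shifts can be read from listings. Under Protocol 8.3.5 the investigator already interprets each ECG and reports clinically significant findings as AEs. The layouts of Tables 3.3.3.4 and 3.3.3.5 are in documents not supplied, so they might show baseline grade.

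Much of this stands, and it rules out several stronger readings that a reader might infer:

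- *That protocol-defined safety results will go unreported.* The values remain. What goes is the protocol's automatic flags and summary tables.
- *That MRD was removed silently.* MRD is an efficacy endpoint, so losing its rate and confidence interval falls within the declared withdrawal of efficacy analyses. Only a listing is missing, because SAP 10.1 promises efficacy listings.
- *That QTcF from a baseline of 420 ms must exceed 525 ms (420 × 1.25) to be picked up.* The outlier rules act above 450 ms.
- *That extra flags are a loss.* PR 120 to 155 ms (35/120 = 29.2%) lies inside Table 29 and is flagged by the SAP. That adds information.
- *That the missing serious-TEAE table and abnormal-ECG listing are undeclared departures.* The SAP body already requires both. SAP 8.1 and 8.2.4 allow listings to replace sparse tables, and Appendix A calls itself a guideline.

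None of this reaches the central point. Neither the Appendix A clause nor the sparse-table clause permits a change of ECG criteria, which is set in the body of the SAP. Investigator judgement is not the predefined criterion that the protocol specified.

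**Conclusion.** The point holds for two safety analyses. SAP 8.5 replaces the Table 29 ECG limits, and SAP 8.3.2 with Appendix A omits the worst-grade and shift tables; SAP 10.1 declares neither. The practical ECG loss is automatic flagging of high PR and QRS and of the low PR, QRS, QT and QTcF limits. For example, a PR just above 220 ms meets the percentage rule only from a baseline below about 176 ms. The laboratory loss is of the protocol's summaries.

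This should be corrected, but the documents do not show that any safety conclusion would change. The finding assumes that Appendix A as supplied is complete and that the unsupplied shells do not restore the missing displays. If Tables 3.3.3.4 and 3.3.3.5 do cross baseline grade with worst grade, the laboratory part narrows to worst grade regardless of baseline and the ungraded tests.

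**What to change.** - **SAP 8.5:** list participants with any value outside Protocol Table 29, in addition to the percentage rule.
- **SAP 8.3.2 and Appendix A:** restore the table of worst postbaseline grade regardless of baseline, the CTCAE shift tables, and the low/normal/high shift tables for ungraded tests.
- **SAP 10.1:** record and justify any departure that remains.
- **Tidy-ups:** add MRD status to the efficacy listings, or state in 10.1 that it is omitted. Add to Appendix A the serious-TEAE table by preferred term and the abnormal-ECG listing.

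The cost is one SAP amendment and a few standard displays from data already collected. By Appendix A's own terms, the two additions to its lists would not need an amendment by themselves.
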